Management Among Adults with Hypertension

- 4.2.** The inclusion criteria will be: adults from 18 to 75 years old, ability to self-consent, English-speaking, able to read/write English, currently prescribed at least one medication for treatment of essential primary hypertension.
- 4.3.** There will be no special populations in this study. This study will not include adults unable to consent; individuals who are not yet adults (infants, children, teenagers); pregnant women; or prisoners.
- 4.4.** Pregnant women will be excluded due to the complexity of hypertension in pregnancy, which warrants management by an OB/GYN or other specialists. Potential participants will be asked if they are pregnant or planning to become pregnant using the screening document “UNM HTN phone screen for potential patients.” Children are excluded for three reasons: 1) the writer is only certified as an NP to work with adults; 2) the focus of this study is the population at greatest risk for high blood pressure which is adults; and 3) children with high blood pressure are rarely diagnosed with essential primary hypertension, and should be managed by a specialist. We do not have the resources to provide adequate materials in Spanish or other languages commonly spoken in NM, and further research may be needed on the effect of the intervention for non-English speaking patients.

5. Number of Subjects

- 5.1.** This is a single site study and will be done at one location, Walgreens Store #6587 in Albuquerque, New Mexico. There will be 50 participants recruited.
- 5.2.** The number to be recruited will be 50.
- 5.3.** Based on statistical analysis from UNM Statistics Department, a sample size of at least 45 patients is needed. The number to be recruited at the onset will be 50 to account for attrition.

6. Study Timelines

- 6.1.**
 - Duration of individual’s participation in research: The total expected duration of participants’ active participation is less than 60 minutes. The participants will have mailed to them at the start of the study: one-page with supplemental handouts/visual aids, list of suggested apps and web sites, pre/post survey and pre/post-test with self-addressed stamped envelopes (SASE) to return their information, and a pill box.
 - Recruitment for this study will begin August-September 2020. Duration anticipated to enroll all subjects: 30 days

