 - Total duration for researchers to complete the study: Recruitment will occur through end of Sept 2020; additional follow-up phone calls will occur through

PROTOCOL TITLE: Evaluating the Effect of an Evidence-Based One Page with
Supplemental Visual Aids on the Knowledge and Perceptions of Blood Pressure
Management Among Adults with Hypertension

September-November 2020. Data analysis will occur during the month of December 2020. Manuscript preparation and submission to scholarly publications will occur shortly thereafter with the target of January 2021.

7. Study Endpoints

- 7.1.** Primary endpoint: change in participant's knowledge of blood pressure management; change in participant's perception of making lifestyle changes to manage their hypertension
- 7.2.** Describe any primary or secondary safety endpoints: N/A
- 7.3.** Describe any exploratory endpoints:
 - 1: Participants will be asked to rate the usefulness, ease of reading, and attractiveness/visual appeal of each handout they were provided.
 - 2: Participants who choose to use any apps or web sites will be asked for feedback on usefulness, ease of reading/access, and attractiveness/visual appeal for each app or web site used.
 - 3: The subset of participants who choose to use electronic resources will be compared to the subset of participants who do not to compare any differences in the primary outcome.

8. Research Setting

- 8.1.** Site or location: Walgreens Store #6587 in Albuquerque, NM.
- 8.2.** We will recruit potential subjects from Walgreens Store #6587 in Albuquerque, NM. Participants will be recruited over the phone.
- 8.3.** Research will be performed from Walgreens Store #6587 in Albuquerque, NM.
- 8.4.** Describe the composition and involvement of any community advisory board: N/A
- 8.5.** This is a partnership with UNM College of Pharmacy, Walgreens Pharmacy, and a Doctor of Nursing (DNP) student enrolled in the DNP program at Missouri State University (MSU). Per MSU policy, once the IRB is submitted and approved through UNM, the IRB approval from UNM with a summary paragraph will be submitted to MSU for record. [name], DNP candidate, will be responsible for submitting the approved UNM IRB with summary paragraph to the MSU IRB board to complete this requirement. A cede letter is included in this submission.

9. Resources Available

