12.2 Patients will be screened for eligibility for the study at Walgreens Store #6587, with pharmacists supervising the PharmD students. Screening will be conducted with the Interview Guide included in this IRB submission as "UNM HTN Prescreen for Potential Participants." Eligible potential participants will have consent forms read and given the opportunity to ask questions about the study. Participants may choose to enroll in the study at that time, or given more time to be mailed consent forms at home and decide at another time. Once the participant consents to participation, the materials will be mailed to the participant, and the participant will complete a pre-survey ("Pre-survey for UNM HTN Study") and pre-test ("Pre-test for UNM HTN Study") on blood pressure management. Participants will be provided a one-page education with supplemental visual aids on blood pressure management with education provided by PharmD students ("My Planned Behavior for Managing My Blood Pressure"). Participants will be provided a list of suggested apps and websites ("Evidence-

PROTOCOL TITLE: Evaluating the Effect of an Evidence-Based One Page with
Supplemental Visual Aids on the Knowledge and Perceptions of Blood Pressure
Management Among Adults with Hypertension

based Websites and Apps for Blood Pressure Management") that they may use if they have a smartphone and/or internet access.

After an initial teaching phone call performed by a PharmD student, a follow-up phone call will be conducted at week 4 and 8 of the participant's enrollment.

During each phone call, study personnel will use a telephone script titled "Phone Call Script for My Planned Behavior for Managing My Blood Pressure Participants" to discuss blood pressure goals, behavioral changes, and principles of blood pressure management.

At week 8, participants will either answer their questions over the phone or be reminded to complete a post-test ("Post-test for UNM HTN Study") and post-survey ("Post-survey for UNM HTN Study") and mail in using their SASE.

12.3 The information will be collected prospectively and information will be collected at the onset of enrollment, during an initial teaching phone call, during phone calls at week 4, and 8, and from mailed in pre/post-test; pre/post surveys.

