- Post-survey ("Post-survey for UNM HTN Study"): Walgreens Store #6587. The purpose of this survey is to gauge the participant's perspectives on engaging in behavioral changes after the educational intervention. The patient may return the completed test by mail, or answer the questions over the phone if they are unable to mail their responses.

13 Data Analysis

- 13.1 Descriptive statistics will be used with demographic information, and paired t-tests will be used for the pre/posttest and pre/post surveys. The UNM Statistics Department will assist with statistical analysis.
- 13.2 Power analysis completed for the paired t-tests to detect difference in pre/post tests and surveys using: one tail, moderate effect size of 0.5, alpha probability of error of 0.05, and power standard of .95 resulted in n=45 (GPower, 2019).

14 Provisions to Monitor the Data to Ensure the Safety of Subjects

N/A. This study poses minimal risk to the patient as it utilizes only non-invasive screening interventions (education; surveys; follow-up phone calls).

15 Withdrawal of Subjects

- 15.1 A patient may be withdrawn from the study should they no longer meet inclusion criteria (for example, if they become pregnant during the study). The patient may also be withdrawn if they are not following the study protocol as agreed upon at the onset of the study. Should the patient no longer be able to be contacted after three phone call attempts, they will be withdrawn from the study. Data obtained up to that point of no contact will be maintained, and used for the study analysis.
- 15.2 The completion of this study will be on the final call to gather data & final post-test and post-survey from the participant. If the patient did make a behavior change of taking blood pressure at home, we will inquire at this time. Upon completion of the study, the participant will be encouraged to continue to see their primary care physician or other medical provider for continued blood pressure management.

PROTOCOL TITLE: Evaluating the Effect of an Evidence-Based One Page with
Supplemental Visual Aids on the Knowledge and Perceptions of Blood Pressure
Management Among Adults with Hypertension

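### Does the comparison of app and website users with non-users need a named between-group method in the analysis section?

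*Combined protocol and SAP*

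**What the plan says.** Section 7.3 lists three exploratory endpoints. The third reads "The subset of participants who choose to use electronic resources will be compared to the subset of participants who do not", and the quantity compared is the primary outcome, defined in 7.1 as "change in participant's knowledge of blood pressure management; change in participant's perception of making lifestyle changes to manage their hypertension".

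Use of the electronic resources is not assigned. Section 12.2 gives participants a list of apps and websites "that they may use if they have a smartphone and/or internet access".

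On analysis, section 13.1 says "Descriptive statistics will be used with demographic information, and paired t-tests will be used for the pre/posttest and pre/post surveys", and adds that the university statistics department will assist. Section 13.2 sizes the paired tests only: "one tail, moderate effect size of 0.5, alpha probability of error of 0.05, and power standard of .95 resulted in n=45". Section 5.3 recruits 50 so that 45 remain after attrition.

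Section 13 contains no between-group test, covariate adjustment or interpretive caution for endpoint 3, and use is not formally defined. Exploratory endpoint 2 does ask participants for feedback on each app or website they used, so user status will be recorded in practice.

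**The concern.** Two features together look like a fault.

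First, the only inferential test named cannot do the job. A paired t-test compares each person with himself or herself and cannot compare two separate sets of people. An analyst limited to it might test users and non-users separately and take a significant result in one and not in the other as evidence of a difference. That inference is wrong, and with small subsets it would often mislead.

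Second, the groups select themselves. Access to a smartphone or the internet may go with age, income and prior knowledge, so a difference in improvement could reflect who chose the apps and not what the apps did.

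At stake is a published statement that the electronic resources add benefit, or add none, when the data support neither.

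**Working it through.** **The plan's own figure.** Inputs from 13.2: one-sided alpha 0.05, standardised effect 0.5, power 0.95. The exact power of a one-sided paired t-test is P(T > t[0.95, n−1]), where T is noncentral t with n−1 degrees of freedom and noncentrality 0.5·√n. This gives 0.947 at n = 44 and 0.951 at n = 45, so n = 45 reproduces. With 10% attrition, 45/0.90 = 50, which agrees with 5.3.

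**Separate tests in each subset.** The documents give no split between users and non-users, so the splits below are assumptions. Suppose the true effect is 0.5 in both subsets, so that there is no difference to find. With powers p₁ and p₂, the chance that exactly one test is significant is p₁(1−p₂) + p₂(1−p₁).

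| Split of 45 | p₁ | p₂ | Exactly one significant |
|---|---|---|---|
| 20/25 | 0.695 | 0.783 | 0.389 |
| 15/30 | 0.578 | 0.848 | 0.446 |
| 10/35 | 0.427 | 0.895 | 0.557 |

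For 20/25: 0.695 × 0.217 + 0.305 × 0.783 = 0.151 + 0.239 = 0.390, or 0.389 before rounding the powers. The rate also depends on the effect. For splits from 23/22 to 35/10 it is 48% to 52% at an effect of 0.3, and 4% to 25% at 0.8.

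**A direct comparison.** A two-sided 0.05 two-sample t-test on change scores rejects in about 5% of simulated trials when the groups are comparable, at splits of 23/22, 30/15 and 35/10. Its power for a 0.5 SD difference in change is 37% (20/25), 34% (15/30) and 28% (10/35). The difference detectable with 80% power is 0.86, 0.91 and 1.03 SD respectively. The comparison can therefore only be descriptive, whatever method is named.

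**Would baseline adjustment repair the self-selection?** Assume that users start D = 0.5 SD higher, that the within-group pre/post correlation is r = 0.5, that scores have unit SD, and that use has no effect. Two models are plausible.

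- *Stable gap.* Users are D higher both before and after. Expected difference in change: D − D = 0. Expected adjusted difference: D − rD = 0.5 − 0.25 = +0.25 SD.
- *Gap acting only through the pre score.* The post score depends on group only via the pre score. Expected difference in change: rD − D = 0.25 − 0.5 = −0.25 SD. Expected adjusted difference: rD − rD = 0.

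Simulation at 20/25 agrees:

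| Model | Change score rejects | Baseline-adjusted rejects |
|---|---|---|
| Stable gap | about 5% | 13% to 15% across runs |
| Through pre score only | about 13% | about 5% |

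This is Lord's paradox. Regression to the mean produces a spurious 0.25 SD difference in change only under the second model. Smartphone access and age are fairly stable traits, which point at least as much to the first. The documents cannot settle which holds.

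**The case for a change.** The strongest opposing case is that the plan promises a between-group comparison and names no test that can perform it. Help from a statistics department is not a prespecified method. Publication is planned (6.1), and the apps are part of the intervention described in 1.1, so a spurious app finding could reach print. The remedy looks cheap: one sentence naming a regression of the week-8 score on user status, adjusted for the pre score and age, with a confidence interval, reported as an association. Pre scores and date of birth are already collected.

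Part of this stands. The method is unstated, use is not defined, and a result from self-selected groups supports association only. The 39% to 56% range is also correct arithmetic for the analysis it describes.

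The rest does not carry. The plan says that "paired t-tests will be used for the pre/posttest and pre/post surveys", which is the primary within-person analysis, where the paired test is the right one. Nothing assigns it to endpoint 3, and the wording of 7.3 describes one subset set against the other. The large error rate therefore belongs to a misuse inferred from silence. The proposed regression is not a clear improvement either. It exchanges one possible bias for another of the same size, and adding age helps only as far as age explains the gap. Naming any method leaves both the low power and the unmeasured confounding in place.

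**Conclusion.** No change is called for. Section 13 leaves the method for exploratory endpoint 3 unstated, and the natural reading is a direct two-group comparison of change. A statistician would run it that way, with a false-difference rate of about 5% when the groups are comparable. The 39% to 56% rate applies only if the subsets are judged by separate one-sided paired tests, at a true effect of 0.5 and the assumed splits. The choice between change scores and baseline adjustment is a fair trade-off in non-randomised groups: each carries a bias of about 0.25 SD under one of the two models, given an assumed 0.5 SD baseline gap and a correlation of 0.5.

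The consequence is small. The endpoint is labelled exploratory, and the working hypothesis in 1.2 treats optional app use as part of the whole intervention and makes no separate claim for it. Neither the primary pre/post analysis nor the sample size of 45 depends on this comparison. The result should be read as an association with chosen use, and nothing in the plan claims more.

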12.4 Initial study activities will occur from the Walgreens Store #6587 in Albuquerque, NM by phone calls: recruitment, enrollment, and initial education. The rest of the information will be gathered by follow-up phone calls at 4 and 8 week intervals, and mail-outs. The phone calls will be made from the Walgreens Pharmacy clinic in a room where the investigator has privacy for the phone calls to speak with the participant.

12.5 Describe, in chronological order, all research procedures and interventions being performed and when they are performed. Include:

- Recruitment: Walgreens Store #6587 by phone
- Screening interview: Walgreens Store #6587 by phone
- Verbal consent and enrollment: Walgreens Store #6587 by phone
- One-page educational intervention ("My Planned Behavior for Managing My Blood Pressure (One Page Handout)") with supplemental visual aids ("DASH diet," "AHA Healthy for Good," and "AHA Blood Pressure Management") will be sent to the mailing address given by the participant with a self-addressed stamp envelope in order to return pre/post-test and pre/post-survey.
- One-page educational intervention with supplemental visual aids: from Walgreens Store #6587 via mail. Education on blood pressure management will be provided to the participant by PharmD students via a phone call after enrollment once patient receives items in the mail. ("Phone call Script for My Planned Behavior for Managing My Blood Pressure Participants").
- Follow-up phone calls at 4 and 8 week intervals: Phone calls will be made to the phone number provided by the participant. Phone calls will be made from private rooms at Walgreens Store #6587. Study personnel will use a phone script ("Phone call Script for My Planned Behavior for Managing My Blood

PROTOCOL TITLE: Evaluating the Effect of an Evidence-Based One Page with Supplemental Visual Aids on the Knowledge and Perceptions of Blood Pressure Management Among Adults with Hypertension

Pressure Participants") to discuss blood pressure goals, behavioral changes, and principles of blood pressure management.

- Post-test on blood pressure management ("Post-test for UNM HTN Study"): Walgreens Store #6587. The purpose of this test is to determine the participant's knowledge of blood pressure management after the educational intervention. The patient may return the completed test by mail, or answer the questions over the phone if they are unable to mail their responses.

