26.2 N/A

26.3 N/A

27 Study Test Results/Incidental Findings

27.1 Individual Results will be from each participant's responses to their pre/post-test and pre/post survey, and responses to the phone script used during initial, week 4, and week 8 phone calls.

27.2 Incidental Findings: We do not anticipate any incidental findings in this study. Participants have already been diagnosed with hypertension as per the inclusion criteria of the study.

28. Sharing Study Progress or Results with Subjects

28.1 The progress of the study will be verbally shared with the participant during each follow-up phone call and during the final study visit upon the participant's request.

28.2 The results of the study will be shared with the public in the form of plain language summary of research findings when ready for publication. Participants may request a summary of the research findings at the conclusion of the study.

29 Inclusion of Vulnerable Populations

This study will not include vulnerable populations.

30 Community-Based Participatory Research - N/A

31 Research Involving American Indian/Native Populations - N/A

PROTOCOL TITLE: Evaluating the Effect of an Evidence-Based One Page with Supplemental Visual Aids on the Knowledge and Perceptions of Blood Pressure Management Among Adults with Hypertension

32 Transnational Research - N/A

33 Drugs or Devices

33.1 Drugs: The study procedures do not involve drugs. Patients in this study may take medications as part of their blood pressure treatment; however, this study does not involve any intervention for prescribing or providing medications to the participant. Patients will only receive education aimed at behavioral changes that may improve their blood pressure management. While patients may receive their medications from Walgreens as part of their usual course of care, study personnel will not prescribe, modify, or provide patient medications as part of the study intervention. The patient will be encouraged to continue their care with their primary care physician or other medical provider for management of their blood pressure and medications.

Devices: The study is not intended to study the safety of effectiveness any specific device.

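### Do the open order of script and post-test at week 8, and the mix of phone and mail answers, undermine the pre/post comparison?

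*Combined protocol and SAP*

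**What the plan says.** All references are to the combined protocol and SAP.

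- **Script at every call.** Section 12.2: "During each phone call, study personnel will use a telephone script". Section 27.1 confirms this for week 8 by listing "responses to the phone script used during initial, week 4, and week 8 phone calls" among the individual results.
- **Post-assessment.** Section 12.2: "At week 8, participants will either answer their questions over the phone or be reminded to complete a post-test". The post-survey is treated the same way. No order relative to the script is given and no condition is placed on the phone route.
- **Pre-assessment.** Section 12.2: "the materials will be mailed to the participant, and the participant will complete a pre-survey". No phone option is stated at baseline.
- **Usual route.** Section 12.3 describes information coming "from mailed in pre/post-test; pre/post surveys". Section 12.5 says of the post-test: "The patient may return the completed test by mail, or answer the questions over the phone if they are unable to mail their responses". It repeats for the post-survey that participants may "answer the questions over the phone if they are unable to mail their responses".
- **Purpose and sequence.** Under a prompt asking for chronological order, 12.5 lists the post-test and post-survey after the 4- and 8-week calls. It describes the test as measuring "knowledge of blood pressure management after the educational intervention".
- **Supply of forms.** Under 6.1 the pre and post forms are mailed together at the start, and no completion window is stated.
- **Final call.** Section 15.2 places study completion on the final call and describes that call as gathering the post-test and post-survey.
- **Recording and analysis.** The list of collected information in 16.11 names neither mode nor completion date. Section 13.1 specifies paired t-tests only.

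**The concern.** Both primary endpoints (7.1) are changes within one unblinded group. No control group shares a timing or mode effect and cancels it, so such an effect goes straight into the estimated change.

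There are two ways in. First, the script covers the subject matter of the test. A participant tested just after hearing it may score higher than one tested days earlier or later, and mail responders hold the post form from the start. Second, answering a member of the study staff by phone can differ from filling in a form alone, most plausibly on the perception survey, while the baseline was completed on paper.

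Read alone, 12.2 lets staff offer the phone freely, which could make mixed-mode pairs common. If neither mode nor date were recorded, the matter could not be examined afterwards. At stake would be a spurious gain, or a masked real one, on both primary endpoints.

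**Working it through.** **1. The plan's own figure.** Section 13.2 gives one tail, effect size 0.5, alpha 0.05, power 0.95 and n = 45. For a paired t-test, power = P(T > t(0.95, n−1)), where T is noncentral t with n−1 degrees of freedom and noncentrality 0.5·√n.

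- n = 44: power 0.947
- n = 45: noncentrality 0.5 × √45 = 3.354, power 0.951

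The smallest n reaching 0.95 is 45, so the stated figure reproduces. The concern does not touch it.

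**2. What the sections settle when read together.**

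| Question | 12.2 alone | With 12.3 and 12.5 |
|---|---|---|
| Usual mode of the post forms | Phone or mail, no condition | Mail; phone if unable to mail (stated for both instruments) |
| Post-assessment relative to the calls | At week 8 | Listed after the 4- and 8-week calls; test measures knowledge after the education |
| Order inside the week-8 call for a phone responder | Not stated | Not stated |
| Date on which a mailed post form is completed | Not stated | Not stated; reminder at week 8 |

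The first two rows are answered. The last two are open in the visible text.

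**3. Size of what is left.** The phone share p and the shift e of phone relative to mail responders (in SDs of the change score) are assumptions; the documents give neither. With true change d in SD units:

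- mean = d + p·e
- SD = √(1 + p(1−p)e²)
- noncentrality = √45 × mean / SD
- one-sided critical value t(0.95, 44) = 1.680

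With no true change (d = 0):

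| p | e | Bias p·e | Rejection rate (nominal 5%) |
|---|---|---|---|
| 0.10 | 0.2 | 0.02 | 6.5% |
| 0.20 | 0.2 | 0.04 | 8.4% |
| 0.10 | 0.3 | 0.03 | 7.4% |
| 0.20 | 0.3 | 0.06 | 10.5% |
| 0.50 | 0.2 | 0.10 | 16% |
| 0.50 | 0.3 | 0.15 | 25% |

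Example, row 2: mean = 0.20 × 0.2 = 0.04; SD = √(1 + 0.16 × 0.04) = 1.003; noncentrality = 6.708 × 0.04 / 1.003 = 0.267; rejection 8.4%.

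Simulation with fixed phone counts agrees: 5 of 45 at 0.2 SD gives 6.6%, 9 of 45 at 0.2 SD gives 8.3%, and 22 of 45 at 0.3 SD gives 24.4%.

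The 50% rows require staff to ignore the condition in 12.5. Going from row 2 to the last row raises both inputs at once, and wording could affect only the phone share. At a fixed shift of 0.2 SD, moving from 20% to 50% phone takes the rate from 8.4% to 16%.

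If the shift is downward (e = −0.2) and the true effect is 0.5, power falls from 95.1% to 93.6% at 10% phone and 91.7% at 20% phone.

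**4. What a mail-mail sensitivity analysis would add.** The 95% half-width in SD units is t(0.975, n−1)/√n.

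| Pairs | Half-width | Power at 0.5 SD |
|---|---|---|
| 45 | 0.300 | 95.1% |
| 40 (about 10% phone) | 0.320 | 92.8% |
| 36 (20% phone) | 0.338 | 90.3% |

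A bias of 0.02-0.04 SD is far smaller than a half-width of 0.32-0.34 SD. The subset shares 80-90% of its pairs with the full analysis, so it would nearly repeat it and could not test for a shift of that size.

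**The case for a change.** The strongest case for a change is that the gaps are real and cheap to close. Section 12.2 omits a condition that 12.5 states twice. No section fixes the order inside the week-8 call or gives a completion window. Mixed-mode pairs are allowed, and the visible list of data items has no mode or date. In a single-arm study nothing else absorbs a shift. The remedy would be a few sentences and two data fields, with no extra participants.

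All of that stands as description. It does not carry a required change, for four reasons.

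- The difference between 12.2 and 12.5 is one of completeness. The shorter sentence is compatible with the fuller one, and staff following the protocol have the fuller rule.
- Order within a call belongs in the phone script, and dates belong on the test and survey forms. These are named attachments that are not in the document. Section 16.11 summarises categories of information under data management; it is not a data dictionary. Their absence from the visible text does not show that they are absent from the study.
- Section 14 counts the follow-up calls among the interventions. Learning from the week-8 call may therefore be part of the effect being measured. Only a difference between phone and mail responders would be an artefact, and under 12.5 the phone group is the exception.
- A reminder could not enforce one order for mail responders, who hold the post forms from enrolment.

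The point about recording deserves most weight: if the forms carry neither mode nor date, the question cannot be looked at later. That is a matter of running the study well, and it does not alter the endpoint or the test.

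**Conclusion.** The concern describes a gap in detail that study staff and analysts can fill sensibly; it is not a flaw in the plan. Read together, 12.2, 12.3 and 12.5 give a usual mode (mail), a restricted exception (phone for those unable to mail) and a sequence (post-assessment after the calls). What remains is the order within the call for the few phone responders and the exact date of mailed forms.

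Under the 12.5 condition, and assuming 10-20% phone responders with a 0.2 SD shift, the bias is 0.02-0.04 SD, at most 0.04/0.5 = 8% of the planning effect. Those inputs are assumptions; the true share, size and direction are unknown. The rate of about 25% needs both half the sample on the phone and a shift of 0.3 SD, neither of which has a basis in the documents. Nor is 5% a well-calibrated starting point in an uncontrolled pre/post design, where larger influences go unmeasured. The available analysis remedy could not resolve a shift of the likely size. No change to the plan follows.
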